8.4.9.5 Reporting of SAEs

All SAEs must be reported to IRW by the Investigator immediately and not later than within 24 hours of knowledge of the event regardless of the time that may have elapsed from the time the event occurred to when the Investigator first learns of it. The preferred method of reporting is through the eCRF, but paper versions of the SAE forms are always available on site if for any reason the eCRF cannot be accessed. The completed paper SAE form should be sent to IRW either via email or fax.

The Initial Report should contain as much information as possible, but a minimum the following information:

- subject identification
- treatment specification (blinded information, if code not broken)
- adverse event diagnosis
- time specification for the medical event
- name of the original reporter

A Serious Adverse Event Report Form must also be completed, signed by the Investigator and submitted to IRW no later than five calendar days after the initial information was received (preferably through the eCRF). Apart from the information above, this Follow-up Report should also contain the following information:

- assessment of severity
- assessment of causality

Investigator shall immediately inform IRW in writing if any of the below occurs (by email to: [contact]):

- (i) any serious adverse event (SAE),
- (ii) any incident,
- (iii) any investigational medical device deficiency that might have led to a SAE,
- (iv) new findings/updates in relation to already reported events, and/or
- (v) any corrective measure.

which occur during the study. When reporting any of the above, the investigator shall provide IRW with details of the product used, the nature of the event/reaction, anonymised patient details, and the details of the person reporting the event/reaction.

SAEs should be reported to IRW even after the study has been finished, if, in the judgment of the Investigator, there might be an association between the event and the previous use of the study product(s) or as a result of the study procedures. The minimum post-study observation period is 5 working days after the Post-study telephone follow-up, but this period can be extended in case the Investigator believe it is necessary.

Only SAEs that are both unexpected and related to the study product(s), Suspected Unexpected Serious Adverse Reactions (SUSARs), are subject to expedited reporting.

The Sponsor is responsible for informing all Investigators concerned of relevant information about SUSARs that could adversely affect the safety of subjects. The appropriate EC and CA, as per local requirements, should be informed by the Sponsor about SAEs associated with the use of the study product/device (SUSARs).

8.4.9.6 Expedited reporting of SUSARs

SUSARs are subject to expedited reporting to CA and EC as defined by local requirements. This includes reactions associated with the study product in the concerned study, or another study with the same study product by the same Sponsor in the EU or in a third country.

Other safety issues also qualify for expedited reporting where they might alter the current benefitrisk assessment of a study product or that would be sufficient to consider changes in the administration of the study product or in the overall conduct of the study.

All SUSARs, which are fatal or life-threatening, must be reported to the applicable CA and EC as quickly as possible but no later than 7 calendar days after the Sponsor/company first became aware of the AE. Additional information on such AE must be reported within 8 days from submission of the first notification.

SUSARs which are not life threatening or fatal must be reported to the applicable CA and EC as soon as possible but no later than 15 calendar days after the sponsor/company first became aware of the AE.

8.4.9.7 Follow-up period after an AE

If a clinical investigation Subject is withdrawn due to an AE, or if an AE persists at the end of the investigation treatment period, this should be followed up until the condition has ceased or until the subject is under professional medical care and a potential causality between the study product and the AE has been penetrated. An outcome assessment should be performed when an AE persists.

8.4.9.7.1 Procedures in case of pregnancy

All pregnancies (either through maternal exposure or transmission of a product via semen following parental exposure) shall be reported to IRW on a pregnancy notification form immediately and within 24 hours of the knowledge of its occurrence by an investigator or delegate (for pregnancies

occurring during the course of the study or immediately following the end of the study). Because of the possibility the fetus/embryo could have been exposed to the study product through the parent and for the subject's safety, the pregnancy will be followed up to determine its outcome, including spontaneous or voluntary termination, details of birth, presence or absence of any birth defects, congenital anomalies, or maternal and/or newborn complications.

The pregnancy will be recorded and reported by the clinical site to IRW, as Sponsor's representative. Pregnancy follow-up will also be properly recorded to ensure quality and completeness of the data belonging to the study product and will include an assessment of the possible causal relation between the study product and any pregnancy outcome.

8.4.9.8 Coding of AEs

Classification of AEs will be performed by System Organ Class (SOC) and Preferred Term (PT) using the Medical Dictionary for Regulatory Activities (MedDRA), version 21.0 or higher.

8.4.9.9 Appropriateness of measurements

This study utilises standard PK assessments and safety assessments.

8.4.9.10 Periodic Safety Reporting

Not applicable in this clinical study

8.4.9.11 List of foreseeable adverse events and anticipated adverse device effects

Please see section/document for Risks and anticipated adverse device effects.

8.5 Data quality assurance

Designated personnel from the BAT quality assurance unit(s) will be responsible for maintaining QA of the clinical, PK, statistical and bioanalytical facilities to ensure that the study is conducted and data are generated, documented and reported in compliance with the protocol, ICH Guideline E6 for GCP, applicable requirements as outlined in the FDA and Organization for Economic Co-operation and Development Principles of Good Laboratory Practice, and the *Reflection paper for laboratories that perform the analysis or evaluation of clinical trial samples* (EMA/INS/GCP/532137/2010).

Designated personnel from each corresponding operation unit (e.g. clinical, PK, statistical and bioanalytical facilities) will be responsible to maintain and assure the QC of all data generated and documented in compliance with the protocol.

8.5.1 Monitoring and auditing procedures

The Study site will be visited by the Monitor periodically at times agreed on by the Investigator and IRW and as defined in the study specific Monitoring Plan. It is the function of the Monitor to ascertain that all aspects of the Study Protocol are complied with and that the conduct of the study conforms to applicable regulatory requirements and established rules for GCP.

At the time of each monitoring visit, the Monitor will review the completed eCRFs to ascertain that all items have been completed and that the data provided are accurate and obtained in the manner specified in the protocol.

The Monitor will also check that the data in the eCRF are consistent with the clinical records (Source Data Verification) and that study results are recorded completely and correctly. The Monitor will check on the reporting of SAEs and the procedures for study product accountability and record keeping. For this purpose, the Monitor must be given direct access to clinical records, original laboratory data, etc., as far as these relate to the study and without jeopardising subject integrity. eCRFs for all included subjects must be made available to the Monitor for review.

The study site may also be subject to quality assurance audit by the Sponsor or someone appointed for this task by the Sponsor. A Competent Authority may request to make an inspection of the study site. The procedures of such a visit would be similar to those of a monitoring visit, and data already checked by the IRW Monitor may be checked again. The Investigator is required to inform IRW immediately of an inspection requested by a Competent Authority.

The sponsor or its representative may visit the study facilities at any time in order to maintain current and personal knowledge of the study through review of the records, comparison with source documents, observation and discussion of the conduct and progress of the study. The clinical site will permit study-related monitoring, audits, IEC review, and regulatory inspection(s) by providing direct access to source data/documents.

8.5.2 Case Report Forms (CRFs)

The data required by the protocol is obtained in two ways. Source Documents are used in the clinic as recording devices during procedures. The data is transcribed from source into an electronic data capture software and stored in the secure database for each subject included in a clinical study (i.e., who received a study product). Screen Failure data may be transcribed into the database at the discretion of the sponsor.

Data assembled outside the clinic source (e.g. safety lab data), will be received from a specified external vendor via an electronic data file. The file received encrypted (or posted to a secure File Transfer Protocol) and is stored in a secure folder on a server. The electronic data file(s) are independent of the Electronic Data Capture (EDC) data during the conduct of the study.

The EDC cleaned data will be reviewed, approved and electronically signed by the Principal Investigator or delegate. The EDC data will be output in a CRF format. The external data files will be output in SAS[®] datasets. All data will be included with the final report provided to the sponsor.

eCRFs of a design mutually agreed upon by the Sponsor and IRW will be supplied by IRW. A CRF must be completed and signed electronically for each included subject. All study team members will get formal training on the eCRF system, before the study starts and it will be documented. The Investigator or his delegate should only allow individuals with the required qualifications and training in eCRFs completion to take part in this task. Confirmation of this qualification or training should be available. CRFs should be completed only by authorised persons. This authorisation should be documented.

The CRF should be completed as soon as the data are available or during the subject's evaluation or follow-up visit.

The completed CRFs should be made available for checking of completeness and accuracy before collection by the Monitor as agreed in advance. The original CRFs are the sole property of the Sponsor and should not be copied or made available in any form to a third party, with the exception of authorised representatives of local Competent Authorities, without the written permission from the Sponsor

8.5.3 Source Data

Data recorded in the CRF should correspond to the data in the source documents, as applicable. Any discrepancies or notable omissions should be brought to the attention of the Investigator/ study staff. For protection of the confidentiality of subjects participating in the clinical study, only non-ambiguous subject identification numbers should be used for identification of all data reported in the CRF.

8.5.4 Training of study staff

It is the responsibility of the Investigator to ensure that all personnel involved in the study are fully informed of all relevant aspects of the study and have a detailed knowledge of and training in the procedures that are to be executed by them.

All Investigators and staff carrying out observations of primary or other major outcome variables involved in the study should provide a Curriculum Vitae (CV). The Investigator will keep a list of all personnel involved in the study together with their function and study related duties delegated. He/she will ensure that appropriate study related training is given to all of these staff, and that any new information of relevance to the performance of this study is forwarded to the staff involved.

Before inclusion of subjects the Monitor and/or Project Manager will perform a Site Initiation Visit to inform and train relevant study staff.

Should an investigator delegate the supervision of the product administration to a designated person, this individual must have the appropriate professional-legal qualifications and certifications. An investigator should also ensure key staff personnel have the appropriate medical qualifications to effectively conduct or supervise any potential resuscitation procedures.

8.5.5 Adherence to Protocol

Excluding an emergency situation in which proper treatment is required for the protection, safety and well-being of the study subjects, the study will be conducted as described in the approved protocol and performed according to ICH/GCP and the applicable regulatory requirements. Any deviation from the protocol will be recorded and explained.

If amendments to the protocol and/or amendments or revisions to the ICF are required, the modifications will be documented and submitted to an IEC for approval.

8.6 Statistical methods and determination of sample size

8.6.1 Demographics and baseline data

Listings and descriptive summary statistics of demographic (age, height, weight and BMI) and baseline data will be presented.

8.6.2 Analysis of pharmacokinetic data

8.6.2.1 Subjects to be Analysed

Samples from all subjects who received at least one of the products will be assayed and nicotine plasma levels will be reported.

8.6.2.2 Bioanalytical Methods

Nicotine plasma concentrations will be measured according to a validated bioanalytical method.

8.6.2.3 Calculated parameters

 C_{max} , T_{max} and AUC_{0-6h} will be calculated from the PK data. Methodology of AUC calculation will be described in the SAP.

8.6.3 Analysis of safety

8.6.3.1 Safety Endpoints

The safety endpoints are the incidence of AEs, vital sign abnormality assessments, clinical laboratory abnormality assessments, symptom-oriented physical examination findings, and oral mucosa examination findings.

8.6.3.2 Safety Analysis

The clinical laboratory tests, the symptom-oriented physical examination, oral mucosa examination and the measurements of vital signs will be used to perform the safety statistical analysis.

8.6.3.3 Safety Statistical Methodology

Descriptive statistics will be used to summarise AEs and safety results.
- 8.6.4 Statistical/analytical issues
- 8.6.4.1 Adjustments for covariates

Possible confounding factors are gender and age. SAP will describe the method of analysis in detail.

- 8.6.4.2 Handling of dropouts or missing data Any missing PK data will not be replaced.
- 8.6.4.3 Multi-centre studies Not applicable
- 8.6.4.4 Multiple comparison/multiplicity Multiple comparisons adjustment must be used during the statistical analysis. Details of comparisons and adjustments will be presented in the SAP.
- 8.6.4.5 Examination of subgroups Subgroups by age and gender will be analysed.
- 8.6.4.6 Interim analyses and data monitoring No interim analyses planned.
- 8.6.5 Analysis data sets

8.6.5.1 Pharmacokinetic Population

The decision of which subjects will be included in the PK analysis is to be documented before the start of the sample analysis. Subjects who received at least one of the study products and are expected to provide evaluable PK data for at least one study product will be included in the PK analysis. Concentration data of any remaining subjects will be presented separately.

The PK population will be further described in the SAP.

Subjects who do not complete the sampling schedule of one or more study periods may be included in the PK analysis for only the PK parameters that are judged not to be affected by the missing sample(s).

8.6.5.2 Safety Population

The safety population will include all subjects who received at least one PK session product administration.

The number of subjects who were included, who discontinued, and who completed the study will be tabulated. The primary reasons for discontinuation will be provided.

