During or after the screening visit but prior to admission for the confinement period, the subjects will attend the clinic for a familiarisation session in which they will be given the highest nicotine strength product (Granit Vit Stark 13 mg/pouch). The purpose of this familiarisation session is to ensure the subject tolerates the product with the highest nicotine strength to avoid dropouts due to product intolerance during the PK sampling period. The subject will use the product in the same way they would normally use a smokeless snus product. There will be a 20 minutes duration of use of the product (from the time the subject places the product in their mouth until the time the subject removes the product from their mouth). Subjects who successfully complete this familiarisation session, i.e., those who are willing to use and show no intolerance to the test product, will be allowed to continue in the study. Subjects who already use Granit Vit Stark (13 mg nicotine/pouch) or snus of 13 mg nicotine/pouch or above do not need to attend the familiarisation session.

For each study period, subjects will abstain from all tobacco and nicotine usage for 12 hours prior to product administration. In addition, subjects will fast overnight (no food or drink except water), for a minimum of 8 hours prior to each product administration. In the morning of each study session, Subjects will receive a standardised light breakfast which will be consumed at least one hour before product administration. Subjects will then receive a single product for a fixed period of 60 minutes and undergo a 6-hour PK blood sample collection. For each study period, a total of 13 blood samples (4 mL per sample) will be collected for PK assessments. PK blood samples will be collected prior to product administration (-5 mins) and at 5, 10, 20, 40, 50, 60, 65, 75, 90, 120, 240 and 360 minutes following product administration.

Subjects are to be discharged from the clinic after the final 6-hour post-administration PK sample collection in each admission period following medical approval. However, they may be advised to stay at the clinical site for safety reasons, if judged necessary by the physician in charge. End of study procedures will be performed prior to discharge from the clinical site.

The duration of the clinical portion of this study per subject (excluding the screening period) is expected to be 10 days. The actual overall study duration may vary.

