8.2 Selection of study population

Subjects who meet all the inclusion criteria and none of the exclusion criteria at the screening visit may be eligible for participation in this study. Continued eligibility will be assessed upon admission to the clinical site, prior to randomisation and the first study product administration.

Screening failures are defined as participants who consent to participate in the clinical study but are not subsequently randomly assigned to the study intervention or entered in the study.

This study will aim to recruit an equal split of males and females. A minimum of 20% females (6 out of 32) will be recruited. This is deemed acceptable based on the Sponsor's demographic data of 2991 Swedish snus users surveyed in 2019, where 81% were male and 19% were female.

A subject who withdraws or is withdrawn during the pre-study evaluations but before receiving the study product will not be considered as a drop-out and will not be included in the final database.

Standbys should be recruited and available to replace any subject who withdraws prior to the first product administration.

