8.2.4 Removal of subjects from therapy or assessment

8.2.4.1 Before First Product Administration

Before the first product administration inclusion/exclusion criteria will govern the subjects to continue to the PK confinement phase. Subjects withdrawn before the first product administration will not be followed up and will not undergo early termination assessments. Other safety assessments may be performed if required.

Subjects are free to withdraw their consent to participate in the study at any time, without prejudice. The reason for their withdrawal or for deciding to end their participation (if the subject agrees to give the reason) will be documented.

All subjects will be informed that they are free to quit smoking and to withdraw from the study at any time.

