8.3 Treatments

8.3.1 Identity of Study Products

The following products will be administered in the study as 60 minute single product administrations.

- 1) Swedish Snus (pouch) Granit Vit Stark with 13 mg/pouch nicotine
- 2) Lyft (Commercial product), 4 mg/pouch
- 3) Lyft (Commercial product), 10 mg/pouch
- 4) Lyft non-commercial (alginate removed), 10 mg/pouch
- 5) Lyft non-commercial (benzoic acid added), 4 mg/pouch
- 6) Lyft non-commercial (benzoic acid added), 10 mg/pouch
- 7) Lyft non-commercial (citric acid added), 10 mg/pouch
- 8) Lyft non-commercial (benzoic acid added, sweet base), 10 mg/pouch

All products will be provided by the sponsor.

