8.4.9.2 Methods for eliciting adverse events

Adverse Events will be collected based on the Investigators' and other study staff's reporting as well as adverse events spontaneously reported by Subjects verbally and/or in questionnaires. All AEs, serious and non-serious, will be recorded in the eCRFs.

The following evaluations are to be done by the Investigator in connection with the AE:

- type of event
- seriousness
- degree of severity
- duration (start end)
- action taken
- causality with investigational product
- outcome of the adverse event

For AE reporting purposes no distinction should be made between the study product and any reference/comparator product.

For the purposes of this study, the monitoring period for AEs extends from the signature of the ICF by the subject until the collection of the last blood sample of the study. From screening to the first product administration of the product familiarisation session, AEs will be recorded as screening events or as part of the medical history, as applicable. AEs occurring from the first product administration of the product familiarisation session to the product administration of period 1 will be recorded as product familiarisation session events. AEs occurring after the first product administration (i.e. after the familiarisation session) will be indicated as TEAEs in the clinical study report.

Subjects will be questioned on their health status at the beginning of each study period and before each departure from the clinical site. Open-ended questions will be asked.

During the study, all AEs spontaneously reported by the subject, observed by the clinical staff or elicited by general questioning will be recorded for all subjects and reported in the CRF.

If necessary, every effort will be made to obtain an adequate follow-up of the subjects. Should any subject choose to withdraw from the study, they will be advised of the safety precautions to be taken.

Any AE which remains unresolved as of the last visit will require an evaluation and follow-up until the AE has been resolved or a reasonable explanation for its persistence found or is deemed mild and safely resolving.

In the case of AEs deemed related to the product, every effort will be made to determine the final outcome.

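### Subjects who used study product 1 only at familiarisation, some of them stopped for intolerance, fall in no safety denominator, and their database entry and follow-up are unclear

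*Protocol*

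**What the plan says.** **Exposure.** Section 8.1 of the protocol describes a session before admission at which "they will be given the highest nicotine strength product (Granit Vit Stark 13 mg/pouch". Section 8.3.1 lists the same item as study product 1: "Swedish Snus (pouch) Granit Vit Stark with 13 mg/pouch nicotine". On length of use, Section 8.1 says "There will be a 20 minutes duration of use of the product"; the PK sessions last 60 minutes.

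**Selection.** Section 8.1 gives the aim: "The purpose of this familiarisation session is to ensure the subject tolerates the product with the highest nicotine strength". Only willing subjects without intolerance continue. Inclusion criterion 11 (Section 8.2.1) adds being able to follow the instructions. Table 1 places randomisation later, at Admission 1.

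**Safety set.** Section 8.6.5.2 reads "The safety population will include all subjects who received at least one PK session product administration".

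**AE recording.** Under Section 8.4.9.2, AEs between familiarisation use and period 1 "will be recorded as product familiarisation session events".

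**Database.** Section 8.2 says that a subject who leaves during the pre-study evaluations "before receiving the study product will not be considered as a drop-out and will not be included in the final database". Section 8.5.2 stores data for subjects who received a study product, and leaves entry of screen-failure data to the sponsor's discretion.

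**Follow-up.** Section 8.2.4.1 states: "Subjects withdrawn before the first product administration will not be followed up and will not undergo early termination assessments". Section 8.4.9.2 requires any AE unresolved at the last visit to be followed, and Section 8.4.9.7 requires follow-up of a subject withdrawn because of an AE.

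**The concern.** Familiarisation is a real exposure to one of the eight products under study, and its purpose is to find and remove people who react badly to that product. A safety set that starts counting only at the PK sessions leaves out the exposed people who were selected because they did not tolerate it.

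Providing safety data is a stated aim of the study (Sections 5 and 5.1), and AE incidence is a safety endpoint (Section 7.4). A reader of the safety tables would see product 1's AE incidence in a group already filtered for tolerance of product 1, with no companion figure for those filtered out. If their records also depend on the sponsor's discretion, the gap might not be recoverable at reporting.

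**Working it through.** No figure in the protocol is in dispute, so the check has two parts: follow one subject through the rules, then show how the size depends on an assumed failure rate.

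**1. A subject who uses product 1 at familiarisation, is intolerant and is not randomised**

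| Question | Section | Result |
|---|---|---|
| Exposed to a study product? | 8.1, 8.3.1 | Yes, product 1 for 20 minutes |
| Randomised? | 8.1, 8.2.1 (criterion 11), Table 1 | No |
| In the safety population? | 8.6.5.2 | No, because there was no PK-session administration |
| AEs recorded? | 8.4.9.2, Table 1 | Yes, under the familiarisation label |
| Analysis set or denominator for those AEs? | 8.6.3 to 8.6.5 | None named |
| In the database? | 8.2, 8.5.2 | Unclear: kept as someone who received a study product, or discretionary as a screening failure |
| Followed up? | 8.2.4.1, 8.4.9.2, 8.4.9.7 | Depends on what *first product administration* means |

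The third row does not depend on any rate: the number of familiarisation-only subjects in the safety population is 0 by definition.

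The last row turns on a term used in two ways. Section 8.4.9.2 applies *first product administration* to the familiarisation session itself, and then to a later point, after familiarisation, from which AEs count as treatment-emergent. Section 8.2.4.1 uses the term while discussing who continues to PK confinement, which points to period 1, but does not define it.

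**2. Size under an assumed failure rate**

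Inputs: 36 randomised (Section 8.6.8.1). The protocol's own figure reproduces: 32 / (1 − 0.10) = 35.6, rounded up to 36. The failure rate p is not in the protocol and is assumed to lie between 2% and 20%. All 36 are taken to have attended familiarisation; because existing users of 13 mg/pouch or stronger may skip it, the counts below are on the high side for each p.

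Number familiarised = 36 / (1 − p), rounded up. Number left out = that number − 36.

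| p (assumed) | Familiarised | Left out | Left out as share of exposed |
|---|---|---|---|
| 2% | 36/0.98 → 37 | 1 | 1/37 = 2.7% |
| 5% | 36/0.95 → 38 | 2 | 2/38 = 5.3% |
| 10% | 36/0.90 = 40 | 4 | 4/40 = 10.0% |
| 20% | 36/0.80 = 45 | 9 | 9/45 = 20.0% |

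If every subject left out was intolerant and none of the 36 was intolerant in a PK session, the safety set would show 0/36 while the last column gives the figure among all exposed. With 2 intolerant among the 36, the safety set would show 2/36 = 5.6%, against 3/37 = 8.1%, 4/38 = 10.5%, 6/40 = 15.0% and 11/45 = 24.4%. These are upper ends for each p, because some exclusions need not involve an AE. If half of the 4 subjects left out at p = 10% had simply been unwilling, 0/36 would compare with 2/40 = 5.0%.

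**The case against.** The other side has several good arguments.

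- **The events are not lost at source.** AEs are monitored from consent, entered in the eCRF and given their own category, and Table 1 marks AE collection at familiarisation. This stands. What is missing is a set, a denominator and assured retention.
- **A reader might infer that these subjects are dropped from the database.** The text does not establish that. Read plainly, Sections 8.2 and 8.5.2 both turn on having received a study product, and a familiarised subject has. The doubt arises because the same subject is also a screening failure, whose data are entered at discretion.
- **A reader might infer that follow-up is denied.** Section 8.2.4.1 goes on to allow other safety assessments if required, and the AE-specific rules in Sections 8.4.9.2 and 8.4.9.7 can be read alongside it. The passages are unclear together rather than flatly opposed.
- **A reader might say that product 1 safety is seen only in those who tolerate it, or that everyone excluded had an event.** Neither follows. The filter is 20 minutes of use with no fasting required (Section 8.4.3), so reactions in the 60-minute sessions still count, including those of exempt users. Unwillingness or failure to follow instructions also excludes.
- **A reader might infer a bias between products.** In a crossover, the same selected subjects are scheduled for all eight products, and safety is descriptive. Pooling 20-minute exposures to product 1 alone into the by-product tables would make the denominators less comparable, and Table 1 schedules no vital signs, mucosa examination or safety bloods at familiarisation. Keeping run-in exposure out of those tables is defensible.
- **The analysis plan could settle it.** Tabulation can be left there. But Section 8.6.5.1 defers further description of the PK population to the SAP, while Section 8.6.5.2 states the safety population with no such deferral.

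**Conclusion.** The point holds in a limited form. As written, the safety population omits every subject whose only exposure to product 1 was at familiarisation, some of them stopped for intolerance. Product 1's absolute AE incidence is therefore described in a tolerance-selected group. The familiarisation AEs are recorded but have no analysis set or denominator. Database entry is unclear, and so is the fit between Section 8.2.4.1 and the AE follow-up rules.

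The size is unknown. The 1 to 9 subjects shown rest on an assumed failure rate of 2% to 20% and on all 36 having been familiarised. The documents do not support a claim that the events are lost, that all those left out had reactions, or that the comparison between products is biased. The primary PK comparisons are unaffected. The change is worth making because it is cheap and concerns people exposed to a study product.

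**What to change.** 1. Keep the PK-session safety population for the by-product safety tables.
2. Add an any-exposure safety set: all subjects who used any study product, including at familiarisation.
3. Tabulate familiarisation-session AEs separately, with the number familiarised as denominator, and give the reasons for not continuing (intolerance, unwillingness, other).
4. Require database entry for every subject who used any study product, so that this no longer depends on the screen-failure discretion in Section 8.5.2.
5. State whether *first product administration* and *receiving the study product* include familiarisation, and reconcile Sections 8.2, 8.2.4.1, 8.4.9.2, 8.4.9.7 and 8.5.2 accordingly. Which follow-up rule applies is for the sponsor and investigators to decide; the passages need to agree.

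The cost is one added definition, one extra AE table and a few extra records. No visit, procedure or sample size changes.
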